- 4) Have a lifetime or current diagnosis of Psychotic Disorder as assessed by specified Mini International Neuropsychiatric Interview (MINI) 7.0.2 modules.
- 5) Have a past or current diagnosis of Bipolar Disorder I or II or have a past or current diagnosis of Other specified Bipolar and related disorder as assessed by specified MINI 7.0.2 modules.
- 6) Any otherwise not specified medical or psychiatric condition, illness, disorder, or concomitant medication that could compromise participant safety or treatment, as determined by the Principal Investigator and/or Study Physician.
- 7) Participant considered by the investigator as unsuitable candidate for full participation in the study.

Refer to Table 1 & Table 2 (Prenatal & Postpartum) for the full schedule of assessments, and more details in section AIM 3 and AIM 4 Assessments.

Refer to sections Participant Recruitment (Aim 1, 3, 4), Pre-Screening Assessment (AIM 1, 3, 4), Informed Consent Process (AIM 1, 3, 4), Baseline Screening Phone Visit (AIM 1, 3, 4) for detailed information of the enrollment process.

Aim 4 Approach (Stage IB)

Design The objective of Aim 4 is to conduct a preliminary randomized trial to evaluate the effect of BA on abstinence and depression at 4 ½ months postpartum; to demonstrate the feasibility of the smartphone-delivered BA intervention for depressed pregnant smokers during prenatal and through 2 ½ months postpartum, and feasibility of study procedures. We will recruit pregnant smokers in the same manner as AIM 3 (Stage IA). We will employ a randomized, controlled between groups design in which depressed pregnant smokers will be randomly assigned, using a form of adaptive randomization called minimization,¹¹² to either BA or HW. We will stratify treatment assignment by baseline depression, smoking rate and gestational age. The data that are collected will be used to support feasibility of delivering a prenatal and postpartum intervention to depressed pregnant smokers via smartphone and to provide estimates of effect size for planning future fully-powered trials.

Participants We will recruit up to 50 depressed pregnant smokers who are between 18 to 32 weeks gestational age in their pregnancies.

Compensation AIM 4

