AIM 4: mailed a welcome study kit including a smartphone, headphones if the ppt requests them, a reloadable gift card, welcome letter, compensation scheme, staff contacts list, zoom instructions, and a pregnancy collection kit. The participant will be scheduled for an equipment check call to test their study phone and the videoconferencing platform to work out any technical issues prior to their first treatment visit. At Visit 1, after a review of information for final eligibility, if participant remains eligible, she will be randomized into the study. The participant

will be mailed a second kit containing urine collection kits and instructions, a smoking cessation participant manual, their assigned participant treatment materials and additional resources.

The study-specific supplies will be shipped to eligible participants and tracked through eShipGlobal or a comparable system within two business days of completion of the Baseline Screening visit and Visit 1.

If a person is deemed ineligible, she will be notified and may be referred to her physician for local medical/psychiatric care for follow-up, if applicable. Resource information may be provided to a participant if deemed appropriate (Appendices: Texas FQHC list, Texas Mental Health Resources, Texas Sheriff's Departments, Texas Domestic Violence Resources, Smoking Cessation Resources). These resources are intended to be living documents and may be updated in real time if we learn that some of the resources are outdated, or new resources are identified, etc.

AIM 1 & 3: Table 1

	Pre-Screening Assessment		Baseline Screening Phone Visit (V0)		V1	V2	V3	V4	V5	V6	V7	V8	V9	V10 EOT	
					day 1 of treatment										
Timeline						Weekly Treatment Visits									
Begininn of Treatment Week					1	2	3	4	5	6	7	8	9	10	
Ideal Days from V1		-14		-7	0	7	14	21	28	35	49	56	63	70	
Table 1. Screening Assessment Schedule	AIM 1	AIM 3	AIM 1	AIM 3	AIM 3										
Telephone script & screen (basic eligibility)	x	x													
Informed Consent verbal/signed			x	x											
MINI*			x	x											
Childhood Trauma Questionnaire				x											
C-SSRS***			x	x											
TLFB				x	x	x	x	x	x	x	x	x	x	x	
FTND					x										
Smoking History Form				x											
Medical History					x										
Urine Cotinine Test**						x	x	x	x	x	x	x	x	x	
Urine Pregnancy Test				x											
Concomitant Medications (other smoking cessation treatments)	x	x	x	x	x	x	x	x	x	x	x	x	x	x	
OUTCOME MEASURES															
PHQ-9			x	x	x	x	x	x	x	x	x	x	x	x	

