Participant Withdrawal. A withdrawal occurs when an enrolled participant actively withdraws consent for further participation in the study, prior to completion of the protocol. Participants may withdraw consent from the trial at any time at their own request, or they may be withdrawn at any time at the discretion of the investigator for safety reasons. All attempts will be made to conduct all evaluations required by the protocol.

Addressing Negative Birth Outcomes. Preterm and negative birth outcomes are common in low income women, especially those with depression who smoke. We will handle these events in the following manner. Women who do not deliver live births will be allowed to continue postpartum treatment if they wish. We will remove them from the sample and replace them with a new participant. For women who experience preterm birth, we will consider providing additional sessions in the postpartum period to ensure a full treatment dose in these individuals. For women who experience other negative birth outcomes which interfere with participation in the postpartum period, we will attempt to make up for missed sessions by increasing the frequency of sessions within the postpartum treatment timeframe. Should negative birth outcomes cause an imbalance in treatment delivery across treatment conditions, this should be detected in our initial analyses of group differences, which will allow us to treat number of treatment sessions as a confounder if such differences are found to be correlated with outcomes (See Statistical Design and Power, Baysesian Modeling Strategy).

Prenatal.

During the prenatal period, participants of 18-22 weeks gestational age will receive 10 individual sessions of BA or HW. The prenatal HW treatment will be similar to the treatment that was utilized in our previous trial.⁵¹ These women will have 16 weeks to complete their 10 individual sessions.

During the prenatal period, participants of 23-32 weeks gestational age will receive 10 individual sessions of BA or HW. The prenatal HW treatment will be similar to the treatment that was utilized in our previous trial.⁵¹ These women will have 12 weeks to complete their 10 individual sessions.

We may do additional check in calls or text communications with participants to maintain engagement between prenatal and postpartum treatment sessions.

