Postpartum. Following birth, women may have up to a month break before resuming individual sessions, though have the option to resume earlier if preferred. Women will receive an additional 4counseling sessions in postpartum over 6 weeks. The participants will complete 1 follow up visit that occurs 4 ½ months postpartum.

Smoking cessation counseling. Smoking cessation counseling will be delivered during the first 15 minutes of the session in both the BA and HW conditions, and will generally follow the Clinical Practice Guideline,³³ providing specific cessation tips and limited social support and problem solving exercises, that will be supplemented with pregnancy focused material relevant to smoking-related topics in the prenatal and postpartum periods. During the postnatal period, smoking cessation counseling will focus on cessation or relapse prevention, depending on the participant's smoking status. All participants will be provided with printed evidence-based pregnancy-specific cessation materials (*Forever Free...For Baby and Me*)⁹¹ that will serve as an outline during smoking cessation counseling discussions (See Section Aims 1-3 Approach 1

(Stage 1A), Focus Group Procedures and Data Analysis for description of postpartum intervention topics.)

BA. Following the 15-minute smoking cessation counseling component, the 45-minute BA component will focus on increasing engagement in rewarding and adaptive activities, decreasing activities such as avoidance and withdrawal that maintain or increase risk for depression, and solving problems that limit access to reinforcers. Behavioral activation strategies include self-monitoring, scheduling daily activities, rating pleasure and accomplishment, exploring alternative behaviors to achieve goals, and role-playing to address behavioral deficits. Postpartum treatment components may be modified depending on the outcome of Aim 2.

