Rate of recruitment will be calculated as the percentage of eligible participants who are consented to participate.

Retention will be calculated as the percentage of enrolled participants who complete the 4 ½ month postpartum assessments.

Completion of treatment visits will be documented using the participant tracking database. These data will be used to calculate the average number of treatment sessions that participants attend and percentage of participants who complete the prenatal and postnatal treatment protocols.

Completion of study measures will be calculated as the percentage of scheduled assessments completed per visit and percentage of scheduled assessments completed per measure.

Rate of receipt of other smoking cessation, psychopharmacological or psychotherapeutic treatment following enrollment will be recorded in the database.

The rate of technical difficulty with smartphone delivery of treatment and assessments will be calculated as the percentage of treatment and assessment sessions that are interrupted due to technical difficulties with the smart phone.

Verification of pregnancy. Participants will confirm positive pregnancy status through study provided pregnancy test or provide paperwork verifying pregnancy status if the pregnancy test is inconclusive.

Biochemical verification of self-report abstinence will be calculated as the ratio of received urine test results (cotinine and/or anabasine) to number of participants who self-reported abstinence at 4 ½ months postpartum

Acceptability of treatment will be assessed in both participants and therapists (see table of assessments for AIM 4) for timepoints. Participants and therapists will be asked to provide ratings of their satisfaction with the BA and HW interventions. Areas that will be included in these ratings are number of treatment sessions, timing of treatment sessions, and quality of interaction with therapists and study staff (for participants' ratings) and quality of interaction with participants (for therapists' ratings).

Therapeutic alliance will be assessed using the client and therapist-rated Working Alliance Inventory, Short Form at PN2, PN4, PN6, PN8, PN10, PP1 & PP3 visits.¹¹⁶ To maintain boundaries in the therapeutic relationship between therapists and the participants with whom they are working, therapists will not be able to access responses or scores on these instruments. In addition, responses on this instrument will be used in data analyses only.

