
Broadly, the data analytic strategy will use generalized linear and multilevel models (SAS 9.4, R v. 3.5, and Stan 2.17) for both discrete (e.g. smoking abstinence) and continuous (e.g. depression) outcomes.¹³⁸⁻¹⁴⁰ Cross-sectional continuous (depression), dichotomous (smoking abstinence) and time-to-event (retention) data will be evaluated using generalized linear modeling or proportional hazards regression. All analyses will apply intention-to-treat principles with missing imputed as non-abstinent for smoking outcomes. For outcomes other than smoking, Bayesian approaches will implement joint modeling of observed outcomes and the missing data which is robust to ignorable missingness (i.e., MCAR and MAR).¹⁴¹ Sensitivity analyses will evaluate robustness of analytic conclusions to missing data. Non-ignorable missing data patterns will be addressed through pattern-mixture modeling methods.¹⁴² Convergence of Bayesian analyses on the posterior distributions via Monte-Carlo Markov chain (MCMC) will be assessed via graphical (Trace Plot, Autocorrelation Plot) and quantitative (Gelman-Rubin Diagnostics and Effective Sample Size) evidence. Evaluation of posterior distributions will permit statements regarding the probability that effects of varying magnitudes exist, given the data. Specification of diffuse, neutral priors will reflect the initial uncertainty regarding effect sizes. For all generalized linear models, priors for regression coefficients will be specified as \sim Normal ($\mu=0$, $\sigma^2=1 \times 10^4$), level one error variances will be specified as \sim Half-Normal ($\mu=0$, $\sigma^2=1 \times 10^4$). Choice of prior distribution for level two variances will follow Gelman's recommendations.¹⁴³ Bayesian Structural Equation Modeling (**BSEM**) prior specification will adapt recommendations from Muthén and Asparouhov.¹⁴⁴ Priors for the comparison of proportions will be specified as \sim Beta ($\alpha=1.0$, $\beta=1.0$).

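### Randomised women without a live birth are removed and replaced, although the plan applies intention-to-treat to all analyses and nowhere reconciles the two

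*Combined protocol and SAP*

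**What the plan says.** **Randomisation.** The Aim 4 paragraph of the Baseline Screening Phone Visit section places it before birth: "At Visit 1, after a review of information for final eligibility, if participant remains eligible, she will be randomized into the study". Entry is at 18 to 32 weeks' gestation (Eligibility Criteria: AIM 4). The Aim 4 Design section says women "will be randomly assigned, using a form of adaptive randomization called minimization".

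**Removal.** Under Treatment, Addressing Negative Birth Outcomes, the protocol expects such events: "Preterm and negative birth outcomes are common in low income women, especially those with depression who smoke". On treatment it says: "Women who do not deliver live births will be allowed to continue postpartum treatment if they wish". The next sentence is the rule at issue: "We will remove them from the sample and replace them with a new participant".

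**Analysis set.** The Bayesian Modeling Strategy section says: "All analyses will apply intention-to-treat principles with missing imputed as non-abstinent for smoking outcomes". It lists no exception.

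**Follow-up and retention.** The Postpartum section says: "The participants will complete 1 follow up visit that occurs 4 ½ months postpartum". Feasibility Measures: AIM 4 says: "Retention will be calculated as the percentage of enrolled participants who complete the 4 ½ month postpartum assessments".

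**The concern.** Absence of a live birth is an event after randomisation. Dropping women because of it means that the compared groups are no longer the groups that were randomised. The Background links smoking in pregnancy to stillbirth and spontaneous abortion, and depression to fetal death. Removal may therefore be related to both primary outcomes, abstinence and PHQ-9. If removals differ between arms in number or prognosis, the comparison is biased.

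Even without bias, two stated rules yield two analysis sets, and nothing says which one feeds the primary comparison or the go rule. The choice could then be made after outcomes are known. The plan also does not say whether removed women's data are still collected and analysed, how a replacement is allocated, or from which date 4½ months is counted when there is no live birth.

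**Working it through.** **1. Is there reconciling text?** None was found.
- The paragraph on negative birth outcomes ends by allowing session count to be treated as a confounder. That addresses unequal treatment delivery, and removed women would not be in that analysis.
- The sensitivity and pattern-mixture analyses in the Bayesian Modeling Strategy section address missing data, not women taken out of the sample.
- The Participant Withdrawal paragraph covers withdrawn consent and investigator withdrawal for safety.
- No modified intention-to-treat or live-birth set is defined.

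**2. The plan's own calculation, reproduced.** Inputs from the Simulated Example: 30 per arm, 7.6% and 25% abstinent, Beta(1,1) priors. The posteriors are Beta(3.28, 28.72) for HW and Beta(8.5, 23.5) for BA. Integrating gives P(RR>1) = 0.962 and P(RR≥1.5) = 0.849, against the stated 96% and 85%. P(RR>1.25), which the plan does not report, is 0.913.

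**3. How often might the rule be used?** The documents give no non-live-birth rate, so q is assumed to lie between 0.5% and 5%. P(at least one removal) = 1 − (1 − q)^N:

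| q | N = 50 | N = 60 |
|---|---|---|
| 0.5% | 22% | 26% |
| 1% | 39% | 45% |
| 2% | 64% | 70% |
| 5% | 92% | 95% |

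Both N are shown because the Aim 4 Participants text says up to 50 and the statistical section says 60.

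**4. Can one woman change the decision?** P(p_BA > 1.25 × p_HW) with independent Beta(1 + x, 1 + n − x) posteriors. The sample has 25 per arm after replacement. The all-randomised set adds removed women back as non-abstinent.

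| HW | BA | Set | P(RR>1.25) | Decision |
|---|---|---|---|---|
| 3/25 | 6/25 | after removal and replacement | 0.743 | no-go |
| 3/26 | 6/25 | one HW woman kept | 0.763 | go |
| 3/26 | 6/26 | one kept in each arm | 0.742 | no-go |
| 5/25 | 9/25 | after removal and replacement | 0.759 | go |
| 5/25 | 9/26 | one BA woman kept | 0.730 | no-go |

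These counts were chosen near the threshold. Under a logistic model with the plan's Normal(0, 10⁴) coefficient priors, the borderline counts move but the sensitivity is similar. There, 4/25 v 7/25 gives 0.745 (no-go) and 4/26 v 7/25 gives 0.767 (go), while 3/25 v 6/25 is already go at 0.790.

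**5. Overall chance that the two sets disagree.** Quitters in the final sample are Binomial(n, 0.076) for HW and Binomial(n, 0.25) for BA. Removed women per arm are negative binomial at rate q and are added back as non-abstinent. The probabilities of all combinations whose decision differs are summed:

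| q HW | q BA | 25 per arm | 30 per arm |
|---|---|---|---|
| 0.5% | 0.5% | 0.6% | 0.6% |
| 1% | 1% | 1.0% | 1.0% |
| 2% | 2% | 1.6% | 1.5% |
| 5% | 5% | 2.7% | 2.5% |
| 5% | 1% | 3.8% | 3.1% |
| 1% | 5% | 1.6% | 2.1% |

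**6. Effect on the relative risk.** With removed women non-abstinent, the expected RR after removal is (1 − q_HW)/(1 − q_BA) times the all-randomised RR: 0.95/0.99 = 0.96 or 0.99/0.95 = 1.04 for the unequal rates above.

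**7. Retention.** For example, 35/50 = 70.0% in the replaced sample becomes 35/52 = 67.3% if two removed women who were not assessed stay in the denominator.

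**The case against.** The strongest reply is that the removal sentence speaks of the sample, not the analysis set, and may mean replacement for accrual only. That reading is possible, but no text supports it, and the ambiguity is what needs settling.

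The trigger is objective and fixed in advance, so nobody has discretion over who is removed. That is true. The open discretion is over which analysis set is used.

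A live-birth population is defensible for an intervention whose postpartum content concerns newborn health and breastfeeding. This also stands, but such a population must be declared as an exception to intention-to-treat.

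The points on size largely stand. The protocol's statement that events are common covers a wider group than non-live births. Entry at 18 weeks or later excludes earlier losses. At the plan's rates the 3/25 v 6/25 outcome itself has a probability of only about 3.2%, and balanced removals change almost nothing.

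Counting every removed woman as non-abstinent is an assumption, since some may continue treatment and quit. If a removed woman is abstinent, one case moves the result further: 5/25 (BA) v 2/25 (HW) gives 0.788, and dropping one abstinent BA woman without replacement (4/24 v 2/25) gives 0.704.

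The timing and retention points are secondary. A delivery without a live birth still has a date, the retention definition read literally keeps all enrolled women, and the 70% benchmark allows exceptions.

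**Conclusion.** The concern holds. The plan removes randomised women after a post-randomisation event, claims intention-to-treat for all analyses, and does not reconcile the two. The size and direction of any bias are unknown, because no non-live-birth rate is given and nothing shows that removals will differ by arm. On the assumptions above, a changed go decision is unlikely: about 0.6% to 2.7% with equal rates, and up to 3.8% with the unequal rates tried. The case rests on an undefined primary analysis population in a trial with small abstinence counts, not on a large expected bias. It should be fixed before outcomes are seen. Confidence is high for the inconsistency and lower for its practical effect.

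**What to change.** Reconcile Addressing Negative Birth Outcomes, the retention definition and the Bayesian Modeling Strategy section:

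- Analyse every randomised woman in her assigned arm.
- State the date from which 4½ months is counted when there is no live birth. Collect outcomes where the woman agrees, and otherwise apply the plan's existing missing-data rules.
- Confirm that she stays in the retention denominator.
- Describe any extra recruit as additional accrual, allocated by the same minimisation procedure.
- Report non-live births by arm, and show a live-birth-only analysis as a labelled sensitivity analysis.

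If the sponsor wants women with live births as the target population, name that exception to intention-to-treat before data are seen and show the all-randomised result beside it.

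The cost is mainly protocol and SAP wording. There may also be a few sensitive follow-up contacts, and total enrolment may exceed the stated maximum by the number of replacements, which the text should allow for. Women who cannot be followed will count as non-abstinent and not retained, so both rates may be slightly lower.

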Participants In years 1 and 2, we will recruit up to 16 participants (half assigned to BA and half assigned to HW who meet the study eligibility criteria (see section Eligibility Criteria), with the exception that we will attempt to recruit women who are between 12 to 34 weeks in gestational age.. This will allow us to pilot test a 10-week course of treatment for BA and HW that may extend into the postpartum period for some women depending on their gestational age at the time of study entry. The participants will be seen during years 1 and 2. Women who participated in focus groups or individual interviews who meet the gestational age eligibility criterion will be offered the opportunity to participate. To encourage completion of screening and treatment sessions, which will allow for more complete collection of pilot data from this limited number of participants, we will compensate women for completing all required questionnaires and applicable samples at each visit. Compensation is as follows: \$25 for screening visit, \$30 for Visit 1, and \$20 for V2-V10, for a possible total of \$235.

Therapist Training In an effort to ensure cultural competence of therapists, study therapists will be required to take a cultural competence course as part of their training. During year 1, [name] and the therapists will complete a virtual in-person training conducted by [name]. This training will include didactic sessions, readings, familiarization with treatment and fidelity rating forms and role playing of BA skills. The therapists will be master level counselors. [name] will work with [name] to develop an ongoing training and supervision plan. Using this plan and under the guidance of [name], Drs. [name] and [name] or [name] will meet with the study therapists on a regular basis for supervision, during Aim 3 treatment delivery and Aim 4 randomized trial treatment delivery. A licensed psychologist or a PI designee will oversee training in HW. Following the BA virtual in-person training and initial pre-certification, and HW training, [name] will deliver the abbreviated 10-session BA protocol to one Stage IA pilot participant. The therapists will deliver both BA and HW 10-session protocols to Stage IA pilot participants. Each session will be videotaped. [name] will provide fidelity ratings on [name] case and will also provide ratings and feedback on the therapist cases. [name]

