GAD-7				x	x	x	x	x	x	x	x	x	x	x	
NICOTINE WITHDRAWAL															
WSWS-28					x	x	x	x	x	x	x	x	x	x	
MEDIATORS															
PANAS				x	x	x	x	x	x	x	x	x	x	x	
PROMIS Cognitive function-abilities				x	x	x	x	x	x	x	x	x	x	x	
OTHER															
Counseling					x	x	x	x	x	x	x	x	x	x	
Adverse Events					x	x	x	x	x	x	x	x	x	x	
WAI-Client Short						x		x		x		x		x	
PROCESS EVALUATION															
Technical issues questionnaire					x	x	x	x	x	x	x	x	x	x	
Barriers to participation interview														x	
Assessment Burden questionnaire						x								x	

* MINI Modules: (A, C, D, E, F, G, H, K, N, O)

**Urine cotinine test will be done at visits where the participant is reporting abstinence and meeting the 7 day point prevalence criteria

***C-SSRS may be done at any visits as clinically indicated by the Safety Plan

AIM 4: Table 2. Prenatal:

Timeline			day 1 of treatment	Prenatal visits (PN)										1 month break after birth of baby
Beginning of Treatment Week			Prenatal visits for GA 18-22 weeks = 10 visits over 16 weeks Prenatal visits for GA 23-32 weeks = 10 visits over 12 weeks											
	Pre-Screening Assessment	Baseline Screening Phone Visit (V0)	PN1	PN2	PN3	PN4	PN5	PN6	PN7	PN8	PN9	PN10		BIRTH
Table 2. Screening Assessment Schedule	AIM 4	AIM 4												
Telephone script & screen (basic eligibility)	x													
Informed Consent verbal/signed		x												
MINI (a)		x												
Childhood Trauma Questionnaire		x												
C-SSRS (b)		x												
TLFB	x	x	x	x	x	x	x	x	x	x	x	x		
FTND		x												
Smoking History Form		x												
Medical History		x												
Urine Test (urine cotinine and/or anabasine collection) - (c)			x	x	x	x	x	x	x	x	x	x	x	
Urine pregnancy test (d)		x												
Concomitant Medications, Other smoking cessation medications_treatments & other Psychotherapy	x	x	x	x	x	x	x	x	x	x	x	x	x	
OUTCOME MEASURES														
PHQ-9		x	x	x	x	x	x	x	x	x	x	x	x	
GAD-7		x	x	x	x	x	x	x	x	x	x	x	x	
NICOTINE WITHDRAWAL														
WSWS-28		x	x	x	x	x	x	x	x	x	x	x	x	
MEDIATORS														
PANAS	x	x	x	x	x	x	x	x	x	x	x	x	x	
PROMIS Cognitive function-abilities	x	x	x	x	x	x	x	x	x	x	x	x	x	
OTHER														
Counseling		x	x	x	x	x	x	x	x	x	x	x	x	
Adverse Events		x	x	x	x	x	x	x	x	x	x	x	x	
Assessment of Changes since last visit			x	x	x	x	x	x	x	x	x	x	x	
FEASIBILITY MEASURES														
WAI-Client Short			x		x		x		x		x		x	
WAI - Therapist			x		x		x		x		x		x	
Technical issues questionnaire		x	x	x	x	x	x	x	x	x	x	x	x	

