Timeline Follow-back Interview (TFBI)¹¹¹ Self-reports of smoking will be collected from participants at baseline using the TFBI. Starting at study entry, self-reported smoking will be collected daily with the Ecological Momentary Assessment (EMA) questionnaire(s) sent to the patients phone through the Qualtrics platform, an MD Anderson-approved secure platform for data collection.

Biochemical verification of pregnancy. If the participant is referred directly from UT Health providers, the provider or designee will confirm pregnancy status through their electronic health record prior to the referral. Participants referred by any other means will confirm positive pregnancy status through an at-home test.

Biochemical verification of self-reported abstinence All participants will be asked to complete a urine cotinine test and send a picture of the results to study staff at each visit (beginning with visit 2) when self-reporting abstinence (Aims 3). To provide preliminary evaluation of the feasibility of collecting these data, we will calculate the ratio of received test results to number of participants who completed sessions 2 through 10. We will use a urine cotinine test that measures nicotine at 100 ng/mL, with a negative result to verify abstinence. We will calculate rate of deception based on the ratio of measures meeting this criterion to self-report of abstinence. Point-prevalence abstinence at the end of treatment will be defined as both a self-report of not smoking during the previous 7 days and a negative result.

Adequacy of participant safety procedures We will gather initial data on the effectiveness of participant safety procedures including ability to screen out participants who are inappropriate for remote delivery of treatment due to safety concerns (e.g., suicide risk, severity of psychiatric symptoms) and ability to provide access to local mental health care when needed.

Therapeutic alliance will be assessed using the client rated Working Alliance Inventory (WAI-C), Short Form at V2, V4, V6, V8, and V10. ¹¹⁶ To maintain boundaries in the therapeutic relationship between therapists and the participants with whom they are working, therapists will not be able to access responses or scores on these instruments.

Feasibility Measures: AIM 4: We will utilize a participant contact tracking database to document number of participants contacted to discuss participation in the study, number eligible, and number who consent to participate.

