AIM 3 and AIM 4 Assessments:

Baseline characteristics of psychiatric disorders/symptoms and nicotine dependence.

The Mini International Neuropsychiatric Interview (MINI) 7.0.2.¹¹⁷ The MINI screens for several DSM-5 Axis I diagnoses. Current Major Depressive Disorder, Past or current Bipolar I or II or Otherwise Specified Bipolar and lifetime or current Psychotic disorder will be assessed using specified modules from version 7.0.2 of the MINI.

The Patient Health Questionnaire - Mood Module (PHQ-9). is a 9 item self-report measure used that was developed to assess the participant's mood over the last two weeks and is used for inclusion and also part of the Safety Monitoring Plan

The Columbia Suicide Severity Rating Scale (C-SSRS) is a measure used to identify and assess individuals at risk for suicide. Questions are phrased for use in an interview format but can be completed as a self-report measure if necessary. This is part of the Safety Monitoring Plan.

The General Anxiety Disorder Scale (GAD 7). The GAD-7 is a validated, seven-item scale developed to assess the presence and severity of generalized anxiety disorder symptoms over the last two weeks and is also part of the Safety Monitoring Plan. Empirically-derived cut-offs can be used to quantify severity of reported symptoms.

The Fagerstrom Test for Nicotine Dependence (FTND)¹¹⁸ is a 6-item scale that will be used to assess nicotine dependence at baseline for Aims 3 and 4.

Biochemical verification of self-reported abstinence Starting after the first treatment session, all participants in AIM 3 will be sent a urine cotinine test at every visit if they self-report abstinence in the last 7 days. In AIM 4, all participants will be sent a urine test (cotinine or anabasine) at every visit if they self-report abstinence in the last 7 days. Participants will be asked to send a picture of the urine test to the research staff via text message or email and/or return the test via mail in the box provided to them. This process is used in several of our

smoking cessation studies and offers the patient a convenient way to provide remote biochemical verification of self-reported abstinence. We will use a urine cotinine test that measures nicotine at 100 ng/mL, with a negative result .

Outcome

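### The Aim 3 test-receipt ratio mixes self-reported abstinence with receipt, because its denominator includes women who were never asked for a test

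*Combined protocol and SAP*

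**What the plan says.** The ratio is defined under Process Measures and Analysis: AIM 3, in the paragraph on biochemical verification of self-reported abstinence. Its purpose is stated there: "To provide preliminary evaluation of the feasibility of collecting these data". The definition is: "we will calculate the ratio of received test results to number of participants who completed sessions 2 through 10".

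Three places say who is tested in Aim 3, and they agree:

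- The same paragraph asks for a test at each visit from visit 2 onward when the woman reports abstinence.
- The double-asterisk note to AIM 1 & 3: Table 1 reads: "Urine cotinine test will be done at visits where the participant is reporting abstinence and meeting the 7 day point prevalence criteria".
- AIM 3 and AIM 4 Assessments states that "all participants in AIM 3 will be sent a urine cotinine test at every visit if they self-report abstinence in the last 7 days".

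The corresponding Aim 4 measure, under Feasibility Measures: AIM 4, is the "ratio of received urine test results (cotinine and/or anabasine) to number of participants who self-reported abstinence at 4 ½ months postpartum". On the size of the pilot, the Aim 3 research design says "we will recruit up to 16 participants".

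**The concern.** The denominator does not match the group that is tested. A woman who attends a visit and reports smoking is not asked for a sample, yet she counts in the denominator and so is treated like someone who failed to return one. The units differ as well: the numerator counts test results, of which one woman can supply several, and the denominator counts women.

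At stake is whether the pilot figure can be interpreted. Preliminary Pilot Testing Procedures says that biochemical verification strategies are among the things to be modified before the randomized trial. A low ratio might mean that remote collection works badly, or only that few women were abstinent. The figure as defined cannot tell these apart.

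**Working it through.** The documents give no value for this ratio, so there is no stated figure to reproduce. The check is algebra on the definition.

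**Inputs**

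- Visits at which a test can be requested: V2 to V10, nine per woman (Table 1).
- Women: up to 16 (Aim 3 research design), so at most 16 × 9 = 144 tests.
- *a* = share of completed V2 to V10 visits with self-reported 7-day abstinence. The documents give no such share. For illustration I use abstinence rates they cite in the Scientific Premise: 7.6% and 13.3% (control and experimental arms of prenatal psychosocial interventions), and 39.2% and 45.3% (end of treatment in the investigators' previous trial). Using these as per-visit shares is an assumption.
- *r* = share of requested tests that are received. Also not given; 1.0 and 0.7 are assumed.

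**Formulas.** Over *n* completed visits, tests requested = *a n* and tests received = *a r n*.

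- Per-visit reading of the definition: *a r n* / *n* = *a r*. Its ceiling, at *r* = 1, is *a*.
- Literal reading (tests over women, all nine sessions completed): 9 *a r*, which runs from 0 to 9 (144/16 = 9).
- Tests requested as denominator: *a r n* / *a n* = *r*, whatever *a* is.

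**Results**

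| *a* | Per visit, *r* = 1.0 | Per visit, *r* = 0.7 | Literal, *r* = 1.0 | Literal, *r* = 0.7 |
|---|---|---|---|---|
| 7.6% | 7.6% | 5.3% | 0.68 | 0.48 |
| 13.3% | 13.3% | 9.3% | 1.20 | 0.84 |
| 39.2% | 39.2% | 27.4% | 3.53 | 2.47 |
| 45.3% | 45.3% | 31.7% | 4.08 | 2.85 |

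With tests requested as the denominator, every row gives 100% at *r* = 1.0 and 70% at *r* = 0.7.

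Two consequences follow. First, on the per-visit reading, good and poor collection can give the same figure: 0.392 × 1.0 = 0.392 and 0.56 × 0.7 = 0.392. Second, on the literal reading the result can pass 1 even when abstinence is low and return incomplete: 9 × 0.133 × 0.9 = 1.08.

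A third reading, in which the denominator is limited to women who completed all nine sessions, does not help. Unless the numerator is limited in the same way, tests sent in by women who later dropped out are counted while those women are not.

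**The case against.** The strongest defence is that the plan already contains most of what is needed. Under Assessment burden it will report, for each measure, the percentage of scheduled assessments that were completed. If a conditional test counts as scheduled only when abstinence triggers it, that is the receipt rate wanted here. The text does not say so, however, and Table 1 marks the cotinine test at every visit from V2 to V10. This softens the problem without curing it. The planned deception rate also takes self-reported abstinence as its base, so the needed count is already foreseen.

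The second defence is weight, and it stands. The a priori feasibility benchmarks are retention and session completion, not test receipt. The specific quantitative plan covers Primary Aim 4 and Secondary Aim 1 only. The Aim 4 receipt measure already conditions on self-reported abstinence.

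Four stronger readings are tempting and are not supported:

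- A reader might infer that the ratio measures abstinence instead of feasibility. It is the product of the two, and at a fixed abstinence share it still falls when tests are not returned.
- A reader might infer that it can never exceed the share reporting abstinence. That holds only per visit; read literally it can exceed 1.
- A reader might infer that it is meant to supply or forecast the Aim 4 receipt figure. The documents give its purpose only as a preliminary look at feasibility in the pilot, and the planned modifications concern procedures.
- A reader might infer that the remedy reproduces the Aim 4 measure. It shares the conditioning but not the unit: Aim 4 counts participants at one time point.

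**Conclusion.** The definition is wrong as written, and the matter is minor. All three statements of the Aim 3 testing rule limit tests to women reporting abstinence, while the denominator has no such limit, and nothing elsewhere clearly resolves this. The result mixes abstinence with receipt. On the cited abstinence rates, perfect collection would show as anything from 7.6% to 45.3% per visit, or from 0.68 to 4.08 tests per woman if read literally. Those ranges rest on the assumed use of published abstinence rates as per-visit shares and show how the definition behaves; they do not predict the pilot. The mismatch itself does not depend on them.

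The reach is one process measure in a pilot of up to 16 women. No decision rule hangs on it, and no Aim 4 outcome changes.

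**What to change.** Replace the definition with: urine cotinine results received, divided by the number of V2 to V10 visits at which the participant self-reported 7-day abstinence (that is, tests requested). This applies the Aim 4 conditioning on self-reported abstinence, but per visit.

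Report the numerator, the denominator and the number of women contributing, because one woman can supply up to nine visits. The denominator may be small: if all 144 visits took place, 7.6% abstinence gives about 11 requested tests (0.076 × 144 = 10.9) and 45.3% gives about 65 (0.453 × 144 = 65.2). It would also help to state under Assessment burden that a conditional test counts as scheduled only when it is triggered.

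The cost is a sentence or two of text. Smoking status is recorded at every treatment visit and test receipt is already to be counted, so no new data, visits or procedures are needed.
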